Study Title: Randomized controlled trial to test the feasibility, acceptability, and preliminary effectiveness of a psychosocial intervention to support Alzheimer's family caregivers in Vietnam.

NCT#: NCT03587974

Document Date: March 1, 2020

Document Type: Statistical Analysis Plan

Statistical Analysis Plan

Characteristics of the caregivers and the care recipients will be compared between the two groups using a two-sample t-test or Chi-square test; the Wilcoxon rank sum test or Fisher's exact test will be used if needed due to violations of the underlying assumptions. Primary analysis of the intervention effect will use an intent-to-treat approach, in which groups were compared based on randomization assignment. To account for the clustering of participants by commune, mixed effects models that included a cluster-specific random effect will be used to estimate differences between groups. Models will utilize the post-intervention assessment as the outcome and included the baseline assessment as a covariate. The post-intervention assessment will be divided by the standard deviation in the entire sample at baseline, so that interpretation of model coefficients will be in terms of standard deviation units. Model assumptions will be checked and met by the data. All analyses will be conducted in SAS, version 9.4, and a *p*-value less than 0.05 considered statistically significant.

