Cases of potential elder abuse/neglect and caregiver suicidal ideation will be handled according to study protocols that are consistent with local practice in Vietnam. Field staff will report all suspected cases of elder abuse/neglect within 24 hours to study investigators [name] (neurologist) and [name] (a geriatrician) at the National Geriatric Hospital. After consultation with the research team including Drs. [name] (a geriatric psychiatrist) and [name] (a social worker), [name] may take additional steps, including contacting and directly assessing the situation, educating family members about abuse, and referring families to local services (e.g. temples, elder clubs, social work services) for counseling and support. Similarly, field staff will report to [name] any caregivers who express suicidal ideation. [name] will then directly contact and assess the caregiver and determine if additional steps are necessary, including referring the caregiver for counseling, support and/or hospital-based mental health and social services. Field staff, usually nurses or social workers, will be trained in these written protocols by the study staff (i.e. [name] and [name]). All cases of elder abuse and caregiver suicidal ideation will be treated as adverse events and discussed at monthly research meetings and reported to each institution's IRB. [name] will report serious adverse events to the SO and NIA.

11) Withdrawal of Subjects

Subjects (patients and family members) may withdraw at any time. If they withdraw from the study, they will be given the option of having their records destroyed.

Page 4 of 8 Revised: February 27, 2017

12) Risks to Subjects

There are two main risks associated with this study: 1) discomfort or mild distress because of the intervention and 2) inconvenience because of the need to fill out the study questionnaires. These risks are similar to the risk of undergoing routine assessments in healthcare clinics in Vietnam. Specific steps are being taken to address each category of risk.

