Discomfort due to the intervention: Even though this study builds on evidence-based strategies for support of family caregivers, subjects may experience discomfort or mild distress when discussing their caregiving experience or because of concerns about confidentiality. These risks are being minimized in several ways. First, caregiver will be given the option of discussing issues privately with the care manager during the intervention. Second, the care manager will be trained to monitor the nature of interactions between patients and family members and any serious issues that emerge will be discussed with the supervising team so that strategies can be developed to address any issues that arise. Finally, subjects will have the opportunity to drop out of the family-centered arm of the study and complete treatment by themselves or drop out of the study altogether.

Inconvenience due to questionnaires: To address the inconvenience associate with completing study questionnaires, we will give subjects the option of completing these in the home or by phone. In addition, during the consent process, participants will be advised that they can choose not to answer any questions that make them feel uncomfortable. Risks to subjects are minimal for several reasons.

This is a behavioral intervention and does not involve drug treatment. In prior studies conducted in the US with multi-cultural populations in the United States there have not been any serious adverse side events attributable to the intervention (personal communication with one of the PIs of a large-scale national study). It is also possible that elder/abuse or neglect may be detected during the study and require intervention. A protocol for handling cases of abuse/neglect according to local norms/resources has been developed in collaboration with our colleagues in Vietnam.

13) Potential Benefits to Subjects

There are several potential direct benefits to subjects. Subject may experience an increase in their knowledge and skills because of the intervention. In addition, caregivers will learn stress reduction techniques that may help reduce caregiving-related distress.

Participants will receive \$10 at the end of each study visit (including both intervention sessions and visits for administration of questionnaires).

Page 5 of 8 Revised: February 27, 2017

14) Multi-Site Research

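### Does the lack of a missing-data rule, with optional destruction of withdrawers' records, undermine the intent-to-treat analysis?

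*SAP*

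**What the plan says.** The SAP is a single paragraph. On the analysis population it says: "Primary analysis of the intervention effect will use an intent-to-treat approach, in which groups were compared based on randomization assignment". On the model it says: "Models will utilize the post-intervention assessment as the outcome and included the baseline assessment as a covariate". On clustering it says: "To account for the clustering of participants by commune, mixed effects models that included a cluster-specific random effect will be used". It mentions no imputation, missing-data assumption, table of losses or sensitivity analysis.

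The protocol foresees that some scores will be missing. Section 11 allows withdrawal at any time and adds: "If they withdraw from the study, they will be given the option of having their records destroyed". Section 12 says that "participants will be advised that they can choose not to answer any questions that make them feel uncomfortable", and that subjects may leave the family-centered arm and carry on alone, or "drop out of the study altogether".

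It also contains measures that support retention. Section 12 says of the questionnaires that "we will give subjects the option of completing these in the home or by phone". Section 13 pays $10 for every session and every questionnaire visit. Section 7 schedules the 3-month assessment in both arms.

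**The concern.** Intent-to-treat is a promise about everyone who was randomised, but a model with one follow-up score per caregiver can analyse only those who supply that score. The intervention arm has 3 to 6 sessions and the control arm has 1, so loss could be unequal. If it were, and if leavers did worse or better at 3 months than their baseline predicts, the estimated effect would be biased in an unknown direction. No planned analysis probes this. The residual checks that the SAP promises use observed scores only and cannot detect it.

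Section 11 seems to make matters worse. If a withdrawer's records go, so does the baseline score needed to check whether the leavers were unusual, and perhaps the note of their allocation. With 25 caregivers per arm, each loss is 4% of an arm. At stake is whether a claim of preliminary effectiveness at p < 0.05 could be produced by selective loss that a reader cannot see.

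**Working it through.** **1. What the model does when a score is missing.** There is one outcome row per caregiver and a random effect for commune only, so a caregiver without a 3-month score contributes no row. This is an inference from the model, not a statement in the SAP. The analysis is then valid, to a close approximation, if loss depends only on arm and baseline score. Imputing the missing scores from those same variables would add essentially no information about the treatment effect. A stated missing-at-random assumption would therefore describe the planned model without altering it.

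**2. How much Section 11 can hide.** There are four routes to a missing score:
- missing the 3-month visit without withdrawing: record kept;
- declining items so that a total cannot be scored: record kept;
- withdrawing without asking for destruction: record kept;
- withdrawing and asking for destruction: baseline data may be lost.

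Only the fourth removes information. Section 11 does not define which records are meant, and Section 7 allocates by cluster, so a commune's assignment does not depend on one caregiver's file. Selective loss might not be fully checkable for this subgroup, but it would not be invisible in general. The final assessment falls at the end of the 3-month participation, so most people who withdraw would have no outcome, and keeping their file would add no row to the primary model. The exception is someone who withdraws after the 3-month assessment. Losing some baselines would also alter the SD used for scaling, but dividing an outcome by a constant changes its units and not its test.

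**3. Size of the possible bias.** The documents have no figure to reproduce: they give no attrition rate, ICC, commune size or effect size. The only documented input is 25 caregivers per arm (Protocol Section 4). The rest is assumed:
- losses of 2 v 1, 5 v 2 or 7 v 2 (intervention v control);
- d, the leaver-minus-stayer gap left after baseline adjustment: 0.5 to 1.0 SD, equal in both arms, with a positive value meaning that leavers are worse;
- baseline correlation 0.5, so the residual variance is 1 − 0.5² = 0.75;
- design effect DE = 1 + (m − 1) × ICC: 1 + 4 × 0.05 = 1.2, or 1 + 11.5 × 0.10 = 2.15.

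Bias in favour of the intervention = (pI − pC) × d, where p is the proportion lost.

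SE = √[0.75 × (1/nI + 1/nC) × DE].

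| Lost | pI − pC | Bias, d = 0.5 | Bias, d = 1.0 | Analysed | SE, DE 1.2 | SE, DE 2.15 | Bias/SE, lowest to highest |
|---|---|---|---|---|---|---|---|
| 2 v 1 | 0.04 | 0.02 | 0.04 | 23 v 24 | 0.277 | 0.371 | 0.05 to 0.14 |
| 5 v 2 | 0.12 | 0.06 | 0.12 | 20 v 23 | 0.290 | 0.388 | 0.15 to 0.41 |
| 7 v 2 | 0.20 | 0.10 | 0.20 | 18 v 23 | 0.299 | 0.400 | 0.25 to 0.67 |

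With d = −0.5 the same losses bias against the intervention by 0.02, 0.06 and 0.10 SD. With equal loss and equal gap the bias is zero. The harshest version of the last row, in which only intervention-arm leavers differ and by 1.0 SD, gives 7/25 × 1.0 = 0.28 SD, or 0.28/0.299 = 0.94 SE. A gap of 1.0 SD after adjustment is large: 1.0/√0.75 = 1.15 residual SDs. Simulated loss that tracked the commune effect gave a bias of 0.00 to 0.11 SD, the top coming from strong loss with ICC as high as 0.20.

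**4. What a delta-shift analysis would add.** Let each arm's delta run from −0.5 to 1.0 SD. For 5 v 2 the shift runs from 0.20 × (−0.5) − 0.08 × 1.0 = −0.18 to 0.20 × 1.0 − 0.08 × (−0.5) = +0.24 SD. The 95% half-width from the same SEs is 1.96 × 0.290 = 0.57 to 1.96 × 0.388 = 0.76 SD. The whole grid sits inside the sampling uncertainty already reported. Its limits come from nothing in the documents, and it varies an untestable assumption without testing it.

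**5. Why error rates are not used as evidence.** With a normal reference, Φ(−1.96 + bias/SE) gives a false-benefit rate of 2.8% to 9.9% over the table, against 2.5% nominal. But DE 2.15 implies 50/12.5 = 4 communes, 2 per arm, where a normal reference fails regardless of missing data. In a simulation with 2 communes of 12 per arm, ICC 0.10, estimated variance and no loss at all, the rate was 5.5% with a normal reference and 0.14% with t on 2 df. In that case the 2.5% starting point does not hold.

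**The case for a change.** The strongest case for a change is this. The gap is real: neither document states a missing-data assumption or commits to reporting loss by arm. A random effect for commune does not make the model robust to dropout. The protocol itself opens the routes to loss and offers unequal contact. The trial tests an effect at p < 0.05, so its pilot status does not excuse it. The remedy would cost a few lines.

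Most of those facts stand, and a reader of the results should expect to see randomised, lost and analysed counts for each arm. They do not carry the conclusion. Feasibility and acceptability are objectives in the protocol title and Section 2, so retention by arm is a result the team needs for its own purposes. Section 10 also has a Safety Officer review study progress and data quality every quarter. That is not a promise of attrition tables, but loss is not unwatched.

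The only proposal that alters a stated rule is to unlink withdrawers' data instead of destroying it. That would trade away a protection offered to participants and would need IRB agreement. It would also come late: Section 5 plans enrolment to the end of September 2018 and 3 months per caregiver, so follow-up should end by December 2018, while the SAP is dated March 2020.

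**Conclusion.** No change to the plan is called for. The SAP is silent on missing 3-month scores, but the model it names already implies a sensible default, and writing that default down would leave the primary estimate as it is. Counts of loss by arm are routine reporting. Optional destruction of records is a fair trade-off between participants' rights and a fuller check on a subset of leavers.

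Under assumed losses up to 7 v 2 and an equal gap of up to 1.0 SD, the bias is at most 0.20 SD, or 0.67 of a standard error. It is 0.28 SD if only intervention-arm leavers differ. At 2 v 1 it is 0.02 to 0.04 SD.

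This rests on assumed attrition, gap, correlation and design effect, none of which the documents give, and on loss by arm being reported. The consent pages and study manual are not in the copy reviewed and may contain retention terms. Heavy, strongly unequal loss would call for caution in reading the result, and the reported counts would show it.
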